8.9. Post-PD Follow-Up Phase

Once subjects experience disease progression and discontinue study treatment, they will be contacted approximately every 3 months (± 14 days), or as needed, by clinic visit or telephone to assess survival and the use of alternative anti-cancer therapy (response to all subsequent anti-cancer therapies including best overall response for each regimen, whether the subject progressed following each regimen, and date of PD if applicable), and other malignancies. Subjects will be contacted until death, subject withdrawal, lost to follow-up, or study termination by the Sponsor, whichever occurs first.

9. SUBJECT COMPLETION AND WITHDRAWAL

9.1. Completion

A subject will be considered to have completed the study if he or she has died before the end of the study, has not been lost to follow up, or has not withdrawn consent before the end of study.

9.2. Withdrawal from Study Treatment

Study treatment will be discontinued in the event of any of the following events:

- Confirmed progressive disease
- Unacceptable toxicity: an intercurrent illness or AE that prevents further study drug administration
- Withdrawal of consent for treatment by subject
- Investigator decision (such as chronic noncompliance, significant protocol deviation, or best interest of the subject)
- Study termination by Sponsor
- Subject becomes pregnant
- Death

Subjects in the Randomization Phase of the MRD cohort or subjects in the Fixed Duration cohort who elect to not reintroduce therapy after confirmed PD, or have a confirmed PD after reintroduction of therapy, will be withdrawn from study treatment.

All subjects, regardless of reason for discontinuation of study treatment will undergo an End -of -Treatment Visit and be followed for progression and survival.

The investigator should notify the Sponsor within 24 hours if a subject discontinues ibrutinib and/or venetoclax treatment due to disease progression and should provide documentation of disease progression for review by the Sponsor's Medical Monitor. If a subject shows signs of disease progression on physical examination or laboratory assessment, the subject may continue study treatment until disease progression is confirmed. These subjects should stay in the study to be followed for survival.

9.3. Withdrawal from Study

Withdrawal from study (including all follow-up) will occur under the following circumstances:

- Death
- Withdrawal of consent for follow-up observation by the subject
- Lost to follow-up
- Study termination by Sponsor

If a subject is lost to follow-up, every reasonable effort should be made by the study site personnel to contact the subject. The measures taken to follow up should be documented.

When a subject withdraws before completing the study, the following information should be documented in the source documents:

- Reason for withdrawal;
- Whether the subject withdraws full consent (ie, withdraws consent to treatment and all further contact) or partial consent (ie, withdraws consent to treatment but agrees to participate in follow-up visits)

10. STATISTICAL METHODS AND ANALYSIS

Statistical analysis will be done by the Sponsor or under the authority of the Sponsor. A general description of the statistical methods to be used to analyze the efficacy and safety data is outlined below. Specific details including the testing procedure for the secondary endpoints will be provided in the Statistical Analysis Plan (SAP).

10.1. Subject Information

The analysis populations are defined as:

All treated populations: defined as all enrolled subjects who received at least 1 dose of study drug in either the MRD cohort or the Fixed Duration cohort and will be used in both efficacy and safety analysis.

MRD-negative randomized population: defined as all subjects in the MRD cohort who achieve confirmed MRD-negative response at the end of the pre-randomization phase and are randomized to either placebo arm or ibrutinib arm for the double-blind treatment. Subjects in this population will be analyzed according to the treatment to which they are randomized.

MRD-positive randomized population: defined as all subjects in the MRD cohort who do not achieve confirmed MRD-negative response at the end of the pre-randomization phase and are randomized to either single-agent ibrutinib arm or ibrutinib + venetoclax combination treatment arm for a prolonged open label treatment. Subjects in this population will be analyzed according to the treatment to which they are randomized.

Pharmacokinetic-evaluable population: defined as all enrolled subjects who received at least 1 dose of study drug and had at least 1 pharmacokinetic sample obtained post-treatment in pre-randomization phase.

██████████ population: defined as all enrolled subjects whose ██████████ is available.

10.2. Endpoints

[figure not shown]
10.2.1. MRD Cohort:

Primary Endpoint:

- 1-year disease-free rate in MRD-negative randomized subjects

Secondary Endpoints:

[figure not shown]
- MRD-negative response rate
- Overall response rate
- Complete response rate (CR / CRi)
- Duration of response
- TLS risk reduction
- Progression free survival
- Overall survival
- Pharmacokinetics of ibrutinib and venetoclax when dosed in combination
- Safety and tolerability

Exploratory Endpoints:**10.2.2. Fixed Duration Cohort:****Primary Endpoint:**

- Complete response (CR/CRi) rate

Secondary Endpoints:

- Duration of response
- MRD-negative response rate
- Overall response rate
- TLS risk reduction
- Progression free survival
- Overall survival
- Safety and tolerability

Exploratory Endpoints:**10.3. Sample Size Determination****MRD Cohort**

The study will be powered based on the primary endpoint of randomization phase, 1-year disease-free rate in MRD-negative randomized subjects (ibrutinib vs placebo). The total sample size will be based on both MRD-negativity clinical response rate from the Pre-randomization Phase and the sample size assumption from Randomization Phase.

Sixty randomized subjects with confirmed MRD-negative status will provide approximately 80% power to detect a 30% improvement in the 1-year disease-free rate, assuming the 1-year disease-free rate is 60% for the control (placebo) arm, at a 2-sided significant level of 0.05.

Assuming a 40% MRD-negative response rate for the ibrutinib and venetoclax combination therapy in the Pre-randomization Phase, 150 subjects will be enrolled in the Pre-randomization Phase in order to have 60 subjects achieve confirmed MRD-negative response and to be randomized. Final sample size may be adjusted based on an early assessment of the MRD-negative response rate among the first 30 subjects who complete 9 cycles of treatment in Pre-randomization Phase (See [Section 3.1.1](#)).

Fixed Duration Cohort

Assuming the CR rate for ibrutinib + venetoclax is 50%, 125 subjects without del17p will provide 83% power to ensure the rate is > 37% at 1-side alpha 0.025. A CR rate of 50% would represent meaningful improvement compared to the CR rate seen with the fixed duration combination of bendamustine + rituximab (31%), and would be an improvement over the CR rate seen with the standard of care fixed duration regimen fludarabine, cyclophosphamide and rituximab (40%) which were obtained in the CLL10 study, which included only patients without del17p ([Eichhorst 2016](#)).

10.4. Efficacy Analysis

In general, the MRD cohort and the Fixed Duration cohort will be analyzed separately. Analysis details will be provided in the SAP.

Descriptive statistics and subject listings will be used to summarize the data. For continuous variables, the number of observations, means, standard deviations, medians, and ranges will be reported. For discrete variables, frequency will be summarized and the 95% confidence interval will be estimated. For time-to-event variables, Kaplan-Meier estimates will be provided. No inferential tests will be performed for pre-randomization phase. The primary endpoint, 1-year disease-free rate in MRD-negative randomized subjects, will be tested between placebo and ibrutinib arms at a 2-sided alpha level of 0.05. All the stratified analyses will be based on the randomization stratification factor, immunoglobulin heavy-chain variable region (IGHV) status.

10.4.1. MRD-Negative Response Rate

MRD-negative response rate is defined as the proportion of subjects who achieve MRD-negativity (definition in [Section 7.2.1.4](#)).

In the MRD cohort, and the Fixed Duration cohort, MRD-negative response rate is the secondary endpoint. The analysis of MRD negativity will be based on the all treated population. [REDACTED] will be summarized as an exploratory analysis.

10.4.2. Disease-Free Survival (DFS)

Disease-free survival (DFS) is the primary endpoint for randomization phase of the MRD cohort and will be analyzed in MRD-negative randomized subjects. DFS is defined as the time that

subjects remain in MRD-negative status without meeting MRD-positive relapse criteria (definition in [Section 7.2.1.4.2](#)), or disease progression (assessed by investigator per IWCLL 2008 criteria) or death from any cause. The primary analysis will be performed when all randomized subjects have had the opportunity to complete at least 12 cycles of randomized treatment or follow-up. 1-year and 2-year disease-free survival rate will be explored. Analysis details will be provided in the SAP.

10.4.3. Overall Response Rate (ORR)

Overall response rate (ORR) is defined as the proportion of subjects who achieve a CR, CRi, nPR, PR, or PRL as evaluated by investigator using IWCLL 2008 criteria. Subjects who do not have any post-baseline response assessment will be considered as non-responders. It is a secondary endpoint for the MRD cohort and the Fixed Duration cohort. [REDACTED] as exploratory endpoints. A pooled analysis in combination with another dataset (eg, CLL3011; GLOW) may be performed for ibrutinib retreatment. Details of the statistical analysis will be described in a separate SAP as applicable.

10.4.4. Complete Response Rate (CRR)

Complete response rate (CRR) is defined as the proportion of subjects who achieve a CR or CRi as evaluated by investigator using IWCLL 2008 criteria. Subjects who do not have any post-baseline response assessment will be considered as non-responders. It is the primary endpoint for the Fixed Duration cohort, and secondary endpoint for the MRD cohort and will be summarized in the all treated population.

10.4.5. Duration of Response (DOR)

Duration of response will be calculated for subjects achieving a response (CR, CRi, nPR, PR) based on IWCLL response criteria and defined as the interval between the date of initial documentation of a response including PR with lymphocytosis, until disease progression or death from any cause, whichever occurs first. Kaplan-Meier methodology will be used to estimate event-free curves, median, and landmark estimates.

10.4.6. Progression-Free Survival (PFS)

Progression-free survival (PFS) is defined as the time from the first dose date of study treatment until disease progression (per IWCLL 2008 criteria) or death from any cause, whichever occurs first.

In the MRD cohort and the Fixed Duration cohort, PFS is a secondary endpoint and will be analyzed in the all treated population. Distribution of PFS will be estimated using Kaplan-Meier method. Median PFS, landmark estimates, and their corresponding 95% CI will be provided.

10.4.7. Overall Survival (OS)

Overall survival (OS) is defined as the time from the first dose date of study treatment until date of death due to any cause.

In the MRD cohort, and the Fixed Duration cohort, OS is a secondary endpoint and will be analyzed in the all treated population. Distribution of OS will be estimated using Kaplan-Meier method. Median OS, landmark estimates and their corresponding 95% CI will be provided.

10.4.8. Tumor Lysis Syndrome (TLS) Risk Reduction Rate

TLS risk reduction rate is defined as the reduction in the proportion of subjects who are at high risk of TLS after the 3-cycle lead-in of single agent ibrutinib, compared to the proportion of patients who are at high risk of TLS at baseline. A reduction in TLS risk from high risk to medium or low risk is clinically meaningful because there is a reduction in the extent of TLS monitoring and risk of hospitalization. TLS risk category is defined in the protocol in [Table 4](#), where Tumor Burden category is equated to TLS risk category. TLS risk reduction is a secondary endpoint for the MRD cohort and the FD cohort, and will be summarized in the all treated population.

10.4.9. [REDACTED]

10.4.10. [REDACTED]

10.4.11. Safety Analysis

In the MRD cohort, analysis of safety data will be conducted on the all treated population in pre-randomization phase and safety population in the randomization phase. An overall summary across both pre-randomization and randomization phase may also be provided as appropriate. The baseline value is defined as the last value collected on or prior to the first dose date of study drug. In the Fixed Duration cohort, safety analysis will be based on all treated population.

The safety variables to be analyzed include exposure of study drugs, AEs, clinical laboratory test results (hematology and chemistry), ECOG performance, physical examination, and vital signs measurements. In general, continuous variables will be summarized using descriptive statistics (n, mean, median, standard deviation, standard error and range). Categorical variables will be summarized using frequencies and percentages. No formal statistical testing is planned.

Adverse Events

Adverse event parameters to be evaluated are the type, incidence, and intensity of AEs; the relationship of AEs to study treatment; and the action taken with respect to study treatment due to AEs.

The verbatim terms used in the eCRF by investigators to identify AEs will be coded using the Medical Dictionary for Regulatory Activities (MedDRA).

Treatment-emergent period is defined as the period of time from the first dose of study treatment, until the earlier of:

- Thirty days following the last dose of ibrutinib or 30 days following the last dose of venetoclax, whichever occurs later

AND

- The start date of a new anti-cancer therapy.

The treatment-emergent AEs (TEAEs) are those events that:

- Are not present prior to the treatment-emergent period and occur during the treatment-emergent period,
- The onset dates are missing, and end dates are during the treatment-emergent period,
- Are considered related to study drug by the investigator regardless of the start dates of the events, or
- Are present prior to the treatment-emergent period but worsen in severity during the treatment-emergent period or are subsequently considered related to study drug by the investigator.

All treatment-emergent AEs will be included in the analysis. For each AE, the number and percentage of subjects who experience at least one occurrence of the given event will be summarized. The number and percent of subjects with TEAEs will be summarized according to intensity (CTCAE, v4.03) or IWCLL for hematologic toxicity, and drug relationship, as well as categorized by system organ class and preferred term. Summaries, listings, datasets, or subject narratives may be provided, as appropriate, for those subjects who die, who discontinue treatment due to an AE, or who experience a severe AE or a SAE.

Clinical Laboratory Tests

Laboratory tests will be summarized separately for hematology and serum chemistry. Local laboratory results will be standardized using the International System SI unit. Selected hematologic and chemistry laboratory parameters are detailed in [Section 7.1.2](#). Hematologic parameters including platelet counts, hemoglobin, and neutrophils will be assessed by the grading scale for hematologic toxicity in CLL studies in the IWCLL 2008 guidelines. All other gradable laboratory parameters will be graded using the NCI CTCAE v4.03.

Unless otherwise specified, only baseline and post-baseline lab values collected during the treatment-emergent period will be included in the analysis. Descriptive statistics will be used.

For selected laboratory parameters, the worst post baseline toxicity grade will be summarized. Analysis for hepatic impairment and renal impairment will be provided.

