5.3.2.1. Randomization Phase – MRD-negative Subjects (Double-blind)

In the Randomization Phase, subjects who are MRD-negative will be randomized in a blinded fashion to ibrutinib or placebo.

Ibrutinib

- Orally once daily ibrutinib 420 mg (3 capsules) continuously until disease progression (post reintroduction when applicable) or unacceptable toxicity

OR**Placebo**

- Orally once daily matching placebo capsules (3 capsules) continuously until confirmed MRD-positive relapse, disease progression, or unacceptable toxicity

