8.2.1.7. Cycle 16 Day 1 Visit**Pre-Dose**

The following procedures will be performed on Day 1 (± 3 days) of Cycle 16:

- Adverse events
- Concomitant medications
- Study drug compliance review
- Physical exam
- Vital signs
- ECOG
- Hematology
- Serum chemistry
- CT/MRI
- Overall response assessment
- Bone marrow biopsy (unless collected prior for CR assessment, and confirmed MRD-negative in BM)
- MRD assessment (bone marrow aspirate and peripheral blood). Bone marrow aspirate can be drawn ± 14 days from C16D1.
- ██████████ assays

Post-Dose

- Dispense ibrutinib and venetoclax for offsite use and provide study drug compliance instructions

MRD Cohort: Randomization Phase

Refer to the Schedule of Assessments ([Appendix A](#)) for a complete list of procedures to be performed at each scheduled study visit.

At Cycle 17 (following 3 cycles of ibrutinib lead-in, completion of 12 cycles of ibrutinib + venetoclax combination treatment, plus 1 cycle to evaluate MRD status) or within 3 days before Cycle 17 Day 1 visit, subjects will be randomized based on their MRD status. Randomization will occur via Interactive Response Technology (IRT) or alternative system provided by the Sponsor.

MRD-neg subjects will be randomized to either **ibrutinib or placebo**, and therapy should be continued until MRD-positive relapse, disease progression, unacceptable treatment-related toxicity, or other reasons outlined in [Section 9.2](#).

Subjects not obtaining confirmed MRD-neg responses (considered MRD-pos) will be randomized to either **ibrutinib + venetoclax or ibrutinib alone**. Ibrutinib and/or venetoclax should be continued until disease progression, unacceptable treatment-related toxicity, or other reasons outlined in [Section 9.2](#).

Central labs for MRD assessment will be used to inform randomization strata, and re-introduction of therapy. Local labs will be used to guide all other dosing-related decisions. In the event of rising MRD assessments, or of clinically suspected disease progression, the subject should continue to receive study medication, at the discretion of the Investigator, until MRD-positive relapse or disease progression is confirmed respectively.

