## **1.4. Sample Size Determination**

### **MRD Cohort**

The MRD cohort is powered based on the primary endpoint of randomization phase, 1-year DFS rate in MRD-negative randomized subjects (ibrutinib vs placebo). The total sample size will be based on both MRD negativity rate from the Pre-randomization Phase and the sample size assumption from Randomization Phase.

Sixty randomized subjects with confirmed MRD negativity will provide approximately 80% power to detect a 30% improvement in the 1-year disease-free rate, assuming the 1-year disease-free rate is 60% for the control (placebo) arm, at a 2-sided significant level of 0.05.

Assuming a 40% MRD negativity rate for the ibrutinib and venetoclax combination therapy in the Pre-randomization Phase, 150 subjects will be enrolled in the Pre-randomization Phase in order to have 60 subjects achieve confirmed MRD negativity and to be randomized.

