### 1.5.2. Primary Analysis

The primary analysis for the MRD cohort will be performed after the last randomized subject has the opportunity to receive 1 year of randomized treatment. All safety and efficacy endpoints for MRD cohort will be analyzed at the time of the primary analysis.

The primary analysis for FD cohort will be performed after the last enrolled FD subject has the opportunity to be followed for at least 30 cycles (15 cycles of treatment + 15 cycles of post-treatment follow-up). All safety and efficacy endpoints for FD cohort will be analyzed at the time of the primary analysis. A longer-term analysis for selected MRD cohort endpoints will also be performed using the same data extraction.

The CSR of this study will describe analyses of both MRD and FD cohorts based on data extracted at the time of FD cohort primary analysis. Results for the primary analysis of MRD cohort with earlier data extraction will also be summarized in a report and be documented in the appendix of clinical study report (CSR).

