**Table 3: Summary of Safety Assessments**

Assessment Type	Definition	Analysis Methods
AE	TEAEs, SAEs, Grade 3 or worse TEAEs, related TEAEs, TEAEs leading to treatment discontinuation, TEAEs leading to dose reduction, TEAEs leading to death, protocol- defined events of special interest and other safety observations.	Descriptive summary statistics and/or listings
Lab	Worst post-baseline toxicity grade for selected gradable hematology and chemistry. Abnormalities in creatinine clearance, uric acid, and liver function.	Descriptive summary statistics and/or listings
Vital Signs	Blood pressure, heart rate	Descriptive summary statistics and/or listings

TEAE= treatment emergent adverse event; SAE= serious adverse event.

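### Adverse events are summarised only as crude percentages although time at risk follows treatment, so if placebo relapses faster, as the plan assumes, equal event rates are expected to look worse on ibrutinib.

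*Protocol*

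**What the plan says.** **Measure.** Protocol section 10.4.11 states that for each adverse event "the number and percentage of subjects who experience at least one occurrence of the given event will be summarized", and adds that "No formal statistical testing is planned" for safety. SAP Table 3 gives the method as "Descriptive summary statistics and/or listings". Neither document plans an event rate, a time-to-first-event summary or a common time window.

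**Window.** SAP section 5 closes the treatment-emergent period 30 days after the last dose, or the day before new antineoplastic therapy or reintroduction, whichever is first. Protocol section 10.4.11 counts 30 days from the last ibrutinib or venetoclax dose, does not name placebo, and does not cut at reintroduction.

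**Periods.** Protocol section 10.4.11 plans a safety analysis for the randomisation phase. SAP section 5 names only the first 16 cycles and the overall period, and SAP section 6 does not record this as a change.

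**Stopping rules, MRD-negative arms.** Protocol section 5.3.2.1 gives placebo as "Orally once daily matching placebo capsules (3 capsules) continuously until confirmed MRD-positive relapse, disease progression, or unacceptable toxicity" and ibrutinib as "Orally once daily ibrutinib 420 mg (3 capsules) continuously until disease progression (post reintroduction when applicable) or unacceptable toxicity". The randomisation-phase text before Protocol section 8.2.2 says for both arms that "therapy should be continued until MRD-positive relapse, disease progression, unacceptable treatment-related toxicity" or other listed reasons apply. SAP section 1.1 also treats both arms until MRD relapse or progression.

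**Planning rates.** SAP section 1.4 powers the cohort for a 30% improvement, "assuming the 1-year disease-free rate is 60% for the control (placebo) arm".

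**Exposure.** SAP section 3.4 summarises ibrutinib and venetoclax exposure and does not name placebo.

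**The concern.** A percentage of subjects with at least one event compares arms fairly only when they are observed for similar times. Here observation ends shortly after treatment ends, and treatment can end at MRD relapse. The trial is planned on the expectation that placebo subjects relapse more often. If that is right, they leave the window earlier and have less time in which to record an event.

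Safety and tolerability is a secondary objective of the MRD cohort. The MRD-negative randomisation is also the trial's only blinded comparison of continuing with stopping ibrutinib. A reader who weighs a treatment holiday will set the DFS result against the toxicity of continued ibrutinib. Part of any excess in crude percentages would then reflect longer observation and not more frequent events.

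**Working it through.** **1. Reproduce the plan's figure.** Inputs (SAP section 1.4, Protocol section 10.3): 60 subjects randomised 1:1, so 30 per arm; placebo 60%; improvement 30%; two-sided 0.05. Taking 30% as absolute gives 90% on ibrutinib. With unpooled variances, matching the SAP's arm-specific Greenwood errors:

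power = Φ(0.30 / √(0.24/30 + 0.09/30) − 1.96) = 81.6%.

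This agrees with the stated 80% or so, so 60% v 90% is the planning scenario.

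**2. Relapse hazards (exponential, an assumption).** Placebo h = −ln 0.6 = 0.511 per year. Ibrutinib h = −ln 0.9 = 0.105 per year.

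**3. Time at risk in randomised year 1.** Both arms stop at the DFS event, the window closes L = 30 days (0.082 y) later, and everyone is cut at 1 year:

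mean = L + (1 − e^(−h(1−L))) / h.

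- Placebo: 0.815 y
- Ibrutinib: 0.957 y
- Ratio: 0.815 / 0.957 = 0.85, or 15% less time on placebo

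This step does not use the wording that lets ibrutinib continue past MRD relapse.

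**4. Crude percentage at the same true rate r in both arms.** The documents give no adverse-event rate, so r = 0.1 and 0.5 per year are assumed. The event-free proportion is

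S = e^(−rL) · h/(h+r) · (1 − e^(−(h+r)(1−L))) + e^(−h(1−L) − r), and the crude percentage is 1 − S.

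**5. The same in the SAP's overall window.** Sixteen common cycles add 16 × 28 / 365.25 = 1.227 y to both arms, so the crude percentage is 1 − S · e^(−1.227r), with r held constant throughout.

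| Window, 1 year after randomisation | r per year | Placebo | Ibrutinib | Ratio |
|---|---|---|---|---|
| Randomised phase | 0.1 | 7.8% | 9.1% | 1.17 |
| Randomised phase | 0.5 | 32.7% | 37.8% | 1.16 |
| Overall | 0.1 | 18.4% | 19.6% | 1.06 |
| Overall | 0.5 | 63.6% | 66.3% | 1.04 |

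**6. What moves the gap (r = 0.5, year 1, 30-day tail dropped for simplicity).**

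- Both arms stop at relapse: 31.5% v 37.5%.
- Ibrutinib never stops: 1 − e^(−0.5) = 39.3%, so the gap widens from 6.0 to 7.9 points (unrounded).
- Both stop and both have 90% disease-free: the gap is 0.
- Ibrutinib withdrawal for other reasons offsets the gap fully at a hazard of 0.511 − 0.105 = 0.405 per year, or 33% in year 1 (40% if ibrutinib otherwise never stops).
- If hazards stay constant to 2 years, the gap with both stopping is 15.1 points.

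**7. Chance of seeing it.** Comparing two binomials of size 30 at the step 6 percentages, ibrutinib has the higher crude percentage in 64% of trials (both stop) to 69% (ibrutinib never stops). Keeping the 30-day tail with both arms stopping gives 61%.

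**8. Does a rate remove it?** Simulated first events per subject-year at a true rate of 0.50 come back as 0.50 v 0.50, while the crude percentages from the same data are 31.4% v 37.5%.

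**The case against.** The strongest reply is that this is a small effect in a descriptive table. At r = 0.5 the gap is about 5 points, or 1.5 subjects of 30, against a standard error of √(0.33 × 0.67/30 + 0.38 × 0.62/30), about 12 points. No safety test is planned. The only by-arm window that the SAP supports is the overall one, where the ratio is about 1.05. Smooth exponential stopping also exaggerates early loss: MRD is scheduled every 3 cycles and relapse needs confirmation. Moving stops to 12-week visits gives a time ratio of 0.89 and 34% v 38%. Ibrutinib stopped for toxicity pulls the other way. All of this stands and limits the size. It does not remove the direction under the plan's own rates, nor supply a summary that allows for exposure. The exposure tables help only in part, because placebo is not named.

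A reader might infer three stronger points that the documents do not support:

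- **That the design makes placebo stop at relapse while ibrutinib continues, so that equal time at risk is impossible.** Protocol section 5.3.2.1 reads that way, but the text before Protocol section 8.2.2 and SAP section 1.1 treat both arms until relapse. Equal time remains possible if relapse rates are equal.
- **That large 3-year distortions are already planned.** SAP section 1.5.2 says "A longer-term analysis for selected MRD cohort endpoints will also be performed using the same data extraction", but it names neither adverse events nor 3 years, and MRD arms may be closed after the primary analysis.
- **That the bias has one known direction under every window.** Under the literal Protocol section 10.4.11 window, a placebo subject who never reintroduces ibrutinib contributes only about 30 days. One who does reintroduce stays in the window, which removes the deficit and counts ibrutinib-era events under placebo.

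**Conclusion.** The point holds in a limited form. The plan offers only crude percentages, the SAP window follows treatment, and under the planned 60% v 90% disease-free rates placebo has about 15% less time at risk in randomised year 1. Equal event rates would then be expected to give a crude percentage about 1.16 to 1.17 times higher on ibrutinib in a randomised-phase window, about 1.04 to 1.06 times in the overall window, and more with longer follow-up.

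This rests on exponential relapse, an assumed constant event rate of 0.1 to 0.5 per year, and no other withdrawal. It does not mean that the ibrutinib arm will show more harm: at 1 year that happens in roughly 61% to 69% of trials of this size at r = 0.5. Nor does it depend on ibrutinib continuing past MRD relapse, which would only widen the gap. The conflicting stopping rules and the two treatment-emergent windows are separate inconsistencies, and both bear on the size of the effect. The change is worth making because it is cheap and removes an avoidable distortion.

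**What to change.** In SAP section 5 and Table 3:

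1. Add the by-arm randomised-phase adverse-event summary that Protocol section 10.4.11 plans. Use one window that starts at the first randomised dose, counts placebo as study treatment and ends at reintroduction in both arms (keeping the SAP's existing 30-day and new-therapy cut-offs). Reconcile Protocol section 10.4.11 with SAP section 5 on this.
2. Beside the crude percentages, report subjects with a first event per 100 patient-years at risk, with 95% CI by arm, for any TEAE, Grade 3 or higher TEAEs, SAEs and the protocol-defined events of special interest. Time at risk ends at the first event or at the end of the window.
3. Show patient-years per arm in the table header, and add placebo to the exposure summary in SAP section 3.4.

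Separately, the stopping rules for the MRD-negative arms in Protocol section 5.3.2.1, the text before Protocol section 8.2.2, and SAP section 1.1 must be reconciled, so that the window has a known end.

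The cost is SAP wording and extra columns from data already collected. The drawback is that a rate assumes roughly constant risk over the window, which is why the crude percentages should stay.
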